This study will be a randomized, placebo-controlled clinical trial enrolling 20 subjects at MCF to either GBP + standard of care (SOC) vs placebo + SOC arm. While enrolling the patients we will stratify patients via numerical pain score (NPS) to either <5 or ≥ 5 . Patients with an NPS ≥ 5 will be randomly assigned to either GBP or placebo group within 72 hours of SAH admission and after informed consent. The SOC pain regimen is comprised of intravenous (IV) fentanyl 25mcg to 50mcg q1hr PRN for head and neck pain as the first-line agent. If SAH pain remains >5 on NPS after the next nursing pain assessment, the next tier of pain agents will be utilized consisting of the following tier:

2nd line- enteral /PO oxycodone 5mg PRN q4hrs pain, and if still in pain after next assessment, then 10mg q4hrs PRN,

3rd line (if 2nd line failed to reduce NPS < 5)- IV 15mg ketorolac q6hrs PRN x 24hrs, unless serum creatinine > 1.3 , or GFR < 30 , or concern for gastrointestinal bleed risk, or history of bleeding peptic ulcer.

4th line (if 3rd line failed to reduce NPS < 5)- dexamethasone 2mg IV BID x 24hrs.

The patient will be enrolled within 72 hours of admission and meeting inclusion criteria by investigator and coinvestigators. Documentation of numeric pain score will be done by standard of care per nursing and hospital policies in the medical record. After consent and enrollment, a data collection sheet will be recorded by nursing to summate the NPS scores every 24 hours along with the SOC pain management plan. The SOC pain management plan will be implemented by the NeuroICU team of residents, attending, and nurse practitioners/PA's who are available on a 24/7 basis. A decrease in pain score equal or more than 50% will be defined as meeting the goal of the study, and as headache pain being under control. Patients will begin study medication (gabapentin or placebo) at approximately 9:00 AM on the morning following randomization into the trial to allow for documentation of the baseline average NPS. The

baseline NPS will be used to determine if the patient has had a 50% or more decrease in pain score.

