In patients with a normal creatinine clearance (CrCl) \geq 60 ml/min the study medication will be started at 100 mg three times a day and if headache is not controlled by study day #2, it will be increased to 300mg three times a day. For headaches that are still not controlled by day 3, study medication will be increased to 600 mg three times a day and by day 4, 900 mg three times a day. For the purposes of this study, a maximal dose of 900 mg tid in patients with normal kidney function (2700mg/day) even though the package insert describes 3600mg/day as maximal. For patients with a CrCl of 30 -59 ml/min, we will use an initial dose of 100mg tid day #1, then 200 mg tid by day #2 if pain uncontrolled, and 400mg tid if by day #3 if pain still uncontrolled. This dose of 1200mg/day would be the maximal dose used for these patients if CrCl remains within the 30-59ml/min range. We will exclude any patients who have CrCl $<$ 30 ml/min. When patients have achieved a 50% reduction of NPS, this will be defined as the maintenance dose and no escalation of GBP will be done after that, unless there is headache worsening. Placebo pills will be given three times a day and SOC pain management performed as indicated above in the control arm. The pharmacist or nurse will dispense the study drug. The bedside nurse will record the numeric pain score (NPS) 0-10, 0 being no pain and 10 being worst pain every 4 hours per hospital policy but done on a bedside data collection form as well for the purposes of the study. Total score over 24 hours will be averaged as daily score. Decision to increase the GBP will be based on 24 hour score communicated by the treating team as part of morning rounds by calling the central pharmacy.

After the 7 day study period, patients will be unblinded to either arm and those on gabapentin may remain on the medication if pain is controlled. However patients in the placebo arm-- if still in pain-- after 7 days may be treated with gabapentin up-titration similar to the treatment arm but used as standard of care. Patient's pain scores will also be recorded after the 7 day randomized period for observational purposes to examine for crossover effect (the proportion of those within the placebo arm who are placed on gabapentin). Analysis of these groups will be based on intention to treat principle.

C.3. Participants

Inclusion Criteria:

1. 18 years of age or older

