2. Have aneurysmal SAH diagnosed by CT scan of the brain and/or angiogram evidence of intracranial aneurysm (CTA or digital subtraction angiogram or MRA)
3. Have symptomatic headache
4. Able to swallow and verbalize pain score
5. No known allergy to GBP or fentanyl
6. Numeric pain score \geq 5
7. Ability to provide written personal consent

Exclusion Criteria:

1. GBP use prior to SAH admission
2. Renal failure with creatinine clearance less than 30 ml/min
3. Unable to receive standard of care pain medications
4. Pregnant patients
5. History of severe depression defined by DSM IV

C.4. Study Procedures & Schedule

All study medication will be labeled and dispensed according to subject number ensuring that treatment assignment remains concealed to the subject, investigator, and all study personnel who have subject contact. Data collection will be done in case report form at the bedside and

later will be enter in spread sheet. We will issue unique ID for each study patients. 20 preprinted study ID labels will be used to randomly select study patients.

Subject selection: All aneurysmal SAH admitted will be screened by the Mayo Cerebrovascular laboratory for eligibility and the NeuroICU attending and/or fellow will be contacted about potential enrollment in the study. Subjects who are able to provide written consent will be approached for enrollment. Based on prior volumes, we expect to have 20 subjects enrolled within 6-9 months.

Pain assessment: We will use numeric pain scale (NPS) that is been validated in many studies and is easy to use. Nurse and medical staff are familiar with this scale in our institute as it has been commonly used as standard of care. We plan to perform this pain scale every 4 hours in the study patients. The scale range from 0-10, 0 being the no pain and 10 being the worst pain ever. We will calculate daily total score for each patient. Only headache and neck pain will be included in the study to calculate the pain score. We will not include the score for other pain like back and abdominal pain.

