Gabapentin escalation dosing will be modeled after our retrospective safety study. We will start with 100 mg orally three times a day then every 24 hours increase to 300 mg tid as tolerated, then 600 mg tid and to a maximum of 900 mg tid. We plan to use 100mg tid then 200 mg tid and 400mg tid if creatinine clearance of 30 -59. We will exclude any patients who have CrCl <30. We will define maintenance dose of GBP as a dose in which after being on it for 24 hours there is 50% reduction of daily average NPS. We will continue maintenance dose throughout hospital stay. aSAH patients will be in observation in NICU for median of 15 days. The placebo will be escalated in the same manner as GBP. A Mayo pharmacist would dispense the study drug (ie., GBP or placebo). Every patients discharged with aSAH will be followed by Mayo neurologist as a SOC and they will plan to reduce or stop GBP.

C.6. Data Analysis

Unless otherwise specified, analyses will be performed using an intention-to-treat approach whereby subjects are analyzed according to randomized treatment arm. The primary endpoint for this trial will be the 7 days of treatment with or without GBP and best medical therapy. For this endpoint the treatment groups will be compared using a two-tailed test with a p -value ≤ 0.05 .

Categorical variables will be summarized as percentages, and continuous factors will be described using means or medians to best describe the distributions. Adverse events will be described as rates, and 95% confidence intervals estimated for those rates. The calculated total daily NPS score; opioid requirement and GBP dose will be analyzed. CSF WBC/RBC ratio will be calculated from the available sample and trended on days of SAH. All the plotted data will be projected with a 95% confidence interval.

We will compare the NPS, patient satisfaction score and the fentanyl requirement among the GBP and placebo group. We will use 2 sample t test or Wilcoxon rank sum test. The data will be analyzed to see if there is difference in incidence of aseptic meningitis, vasospasm and DIND between the GBP and placebo group. If there is difference more than 5 %, we will use regression modeling to analyze the data.

C.7. Sample Size Considerations

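### The NPS outcome is a 24-hour total in some sections and an average in others, with no missed-reading rule, and the recorded baseline is left out of the arm comparison

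*Combined protocol and SAP*

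**What the plan says.** Sections that name a sum:
- C.6: "The calculated total daily NPS score; opioid requirement and GBP dose will be analyzed".
- C.4, Pain assessment: "We will calculate daily total score for each patient". A.2 says the same.
- C.2: the bedside sheet is used "to summate the NPS scores every 24 hours along with the SOC pain management plan".

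Sections that name an average:
- C.2, baseline: the first dose waits until the morning after randomization "to allow for documentation of the baseline average NPS".
- C.2, daily score: "Total score over 24 hours will be averaged as daily score".
- C.5, maintenance dose: reached when "there is 50% reduction of daily average NPS".

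C.7 frames its null hypothesis around a daily NPS score without saying which of the two it is. C.2 adds "Decision to increase the GBP will be based on 24 hour score", again without naming the form.

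Readings are due every 4 hours. No section says what happens when one is missed, or how seven daily values become one value per patient. For the arm comparison C.6 says "We will use 2 sample t test or Wilcoxon rank sum test". The only stated use of the baseline average is to judge the 50% within-patient decrease.

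**The concern.** NPS is one of the two primary aims, yet two analysts following this plan could compute different outcomes. The choice matters only when readings are missed: a sum with no rule gives an absent reading the value 0, which on this scale means no pain, while a mean of completed readings does not. If one arm misses more readings, a test on totals counts that as pain relief.

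Some imbalance is conceivable. Patients must verbalize the score, A.3 describes dose-dependent but typically transient sedation on starting gabapentin, and A.4 links opioids, which both arms receive, to sedation. The documents do not say whether a sleeping patient is woken, skipped or scored.

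A second, separate matter is precision. With 10 patients per arm, a baseline measured before the first dose could sharpen the comparison, and C.6 does not use it.

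**Working it through.** **1. The plan's own figure.** C.7 gives a 25% difference, SD 5.84, alpha 0.05, 80% power and a sample size below 10. C.6 makes the test two-sided. The reference mean and the scale of the SD are not stated, so the figure can only be bracketed. By the normal approximation, n per arm = 2(1.960 + 0.842)² × 5.84² / δ² = 535.4 / δ².
- Total scale (0-60), assumed reference 31: δ = 0.25 × 31 = 7.75, so n = 535.4 / 60.06 = 8.9, rounded up to 9.
- Average scale (0-10), assumed reference 10: δ = 2.5, so n = 535.4 / 6.25 = 85.7, rounded up to 86. Assumed reference 5: δ = 1.25, so n = 343.
- The largest SD possible on a 0-10 scale with the 53 retrospective patients is 5 × √(53/52) = 5.05. So 5.84 cannot be the SD of a 0-10 average. It fits a total or another wider scale.

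**2. Complete data.** 24 / 4 = 6 readings a day, so total = 6 × average. Rescaling by a constant leaves the t and Wilcoxon p-values unchanged.

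**3. Missed readings in one patient.** At a constant NPS of 5, the total is 30 with six readings, 25 with five (1/6 = 17% lower) and 20 with four (2/6 = 33% lower). The average stays at 5.

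**4. The gap between arms.** At an assumed 1.0 versus 0.5 missed per day, 5.0 versus 5.5 readings are completed, so the totals differ by 0.5 / 5.5 = 9%. Over the week this becomes 9% × 4/7 = 5% if the imbalance is confined to days 1-4, and 9% × 2/7 = 3% if confined to days 1-2.

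**5. False rejection.** Simulation of 10 versus 10 patients with 7 days of 6 readings and no true difference. Assumed: mean NPS 5-7, between-patient SD 1-2, within-patient reading SD 1.5. t-test on the total:

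| Missed per day | 7 days | Days 1-4 | Days 1-2 |
|---|---|---|---|
| 1.0 vs 1.0 | 5% | - | - |
| 1.0 vs 0.5 | 8-25% | 6-12% | 5-7% |
| 1.0 vs 0 (extreme) | 16-71% | 9-29% | 6-10% |

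Rounding readings to whole numbers from 0 to 10 moves the upper ends by at most a few points. Wilcoxon is similar (7-22% for 1.0 vs 0.5 over 7 days). The mean of daily means stays at about 5% in every cell, because missingness here is unrelated to pain.

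**6. When missed readings are truly lower.** Assumed 4 points lower, over 7 days:

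| Missed per day | Total | Mean of daily means | Missed set to that day's lowest |
|---|---|---|---|
| 1.0 vs 0.5 | 6-12% | 6-11% | 5-7% |
| 1.0 vs 0 | 6-26% | 10-28% | 7-14% |

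**7. Why average within days first.** C.1.b reports pain rising to about day 5. With an assumed 3-point rise and 2.0 versus 0.5 missed on days 1-4, a mean pooled over all readings differs between arms by 0.14-0.16 points. The mean of daily means differs by less than 0.01.

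**8. Baseline adjustment.** At an effect giving the t-test 80% power with 10 per arm, ANCOVA has power 77%, 79%, 80%, 81%, 88% and 97% at assumed baseline correlations of 0, 0.2, 0.25, 0.3, 0.5 and 0.7.

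**The case against.** The strongest reply is that the tested score may already be an average. C.2 makes the total a step towards an average, C.7 uses C.2's term for the daily score, and the C.6 sentence on comparing arms says only NPS. The word total stands in the descriptive paragraph. This is a fair reading, so a reader should not infer that the plan certainly tests a total. It does not settle the matter, because A.2, C.4 and C.6 name a total outright and the SD in C.7 cannot belong to a 0-10 average.

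The second reply is that the harm is hypothetical. Bedside nurses score every 4 hours under hospital policy, on a study form as well, in patients able to speak. Near-complete data are plausible, and every rejection rate above rests on assumed missingness. That stands.

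A reader might also infer that gabapentin sedation would bias the trial in the drug's favour. The documents do not support this: they give no missing rate or direction, describe the sedation as typically transient, and give opioids to both arms. Nor should the 17% or 33% drop within a patient be set against the planned 25% difference between arms. The comparable figure in the assumed case is 9%.

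On ANCOVA, the unadjusted test is valid in a randomized trial, no baseline correlation is given, and entry at NPS of 5 or more narrows the baseline range. All of that stands. It makes a net gain likely but not shown.

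**Conclusion.** The inconsistency between total and average is certain from the text, and so is the absence of a missed-reading rule and of a 7-day summary. Its effect on the result is conditional. It is nil with complete data or with equal missingness unrelated to pain, near nominal if an imbalance of half a reading per day lasts two days, and material (8-25% false rejection) if it lasts the week and a total is tested. These rates assume the pain levels, SDs and missing rates listed above.

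A mean of completed readings removes the problem when missingness is unrelated to pain. A reader might infer that it removes it altogether, but it offers little or no advantage over the total when missed readings are much lower-pain.

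Leaving out baseline is a question of precision, not bias: about 3 power points lost by adjusting at zero correlation, break-even near 0.25, and 8 points gained at 0.5. The changes should be made, but the trial is not invalid without them. Confidence is medium because the missingness is unknown.

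**What to change.** For the outcome analysis only:
1. Define the NPS outcome as the mean over days 1-7 of each day's mean of completed head and neck readings. Replace the total in C.6, A.2 and C.4, and state what is done on a day with no completed reading. Restate the SD in C.7 on this scale and rework the sample size from it, with the reference mean given.
2. Prespecify ANCOVA with baseline average NPS as covariate for the arm comparison. Keep the unadjusted t or Wilcoxon test as a sensitivity analysis.
3. Report completed readings per day by arm. Repeat the analysis with missed readings set to that patient's lowest reading of the day and, as a bound, to 0. Limit this to asleep readings only if the reason is recorded, which no section currently provides for.

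The readings and baseline are already collected, so steps 1 and 2 need no new data. The costs are the C.7 rework, one degree of freedom for the covariate and, if asleep readings are to be separated, a reason field on the bedside form.

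For dose escalation, the 50% goal and the maintenance dose, the total and average wording in C.2 and C.5 must be reconciled. No rule is proposed there.

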and slowly titrated up to maintenance dose. Gabapentin has been used successfully to treat neuropathic pain and perioperative pain ¹³. It has been shown to reduce stroke size, decrease the cortical spreading depression (CSD), which in turn can cause vasospasm and delayed ischemic neurologic deficit (DIND) ¹⁴. Mayo Clinic Jacksonville has been using gabapentin in order to reduce the narcotic requirement and complication. In our retrospective chart review in neurocritical care ICU (NICU) from January 2011 till February 2013, study (53 patients) there was 6% nausea (intolerable in 1.9%) but no major adverse effects of gabapentin maintenance dose (1800-2700mg /day). We also found a decrease in mean use of opioids with the use of gabapentin within the first 4 days post SAH compared to after 5 days (P = 0.01) . There was no fall, dizziness and abnormal liver function associated with the use of gabapentin. Aseptic meningitis was detected with the analysis of cerebrospinal fluid (CSF) during the second half of the ICU stay. The cost of 300mg of gabapentin was average of 30 times less than intravenous fentanyl 100 mcg. We did not find any other study looking at the use of gabapentin in aSAH patients.

The plan is to conduct a randomized control trial with a total of 20 aSAH patients. 10 aSAH patients admitted in NICU will be assigned to receive gabapentin, and 10 will receive placebo. Both of the groups will receive standard of care for pain control for 7 days.

Hypothesis: “Gabapentin will reduce the pain score and narcotics requirement_among hospitalized aSAH patients compared to placebo alone.”

The primary specific aims and hypothesis of this study are:

1. To compare the narcotic requirements among SAH patients experiencing headache treated with gabapentin or placebo for 7 days.
2. To compare efficacy of gabapentin in reducing the headache numeric pain score (NPS) compared to the non-GBP arm among hospitalized aSAH patients. Both groups are treated by an existing standard of care algorithm with narcotics and NSAIDs.

The secondary aims of this study are:

1. To evaluate the initial dose, escalation and side effects of gabapentin (nausea, vomiting, fall, lightheadedness, dizziness, vertigo, confusion).
2. To evaluate the incidence of delirium, vasospasm, delayed ischemic neurologic deficit (DIND) and seizure among hospitalized aSAH patients.
3. To evaluate the incidence of aseptic meningitis with cerebrospinal fluid (white blood cell and red blood cell ratio).

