Narcotic Requirement: We will use intravenous fentanyl as a pain medication. The dose range of fentanyl will be from 25 micrograms to 50 micrograms, which could be repeated hourly. Total daily requirement of fentanyl for head and neck pain will be calculated every day. The side effects of the fentanyl will be prospectively charted. We plan to use subsequent line of pain management as describe in the text above if not controlled by fentanyl or have side effects with it.

Laboratory variables: Whenever cerebrospinal fluid (CSF) is collected by standard of care via an external ventricular drain or lumbar specimen. We will review this data for white blood cell (WBC), red blood cell (RBC) counts, as well as the CSF WBC/RBC ratio and culture and sensitivity. We will also review values of kidney function (creatinine and BUN), in the medical record performed as standard of care by the treating team.

Radiological variables: We will review patient CT or CT angiography done by standard of care by the treating team. We plan to get SAH severity using the Fisher grade, aneurysm location, follow up CT angiography and/ or transcranial Doppler for detection of vasospasm.

Aseptic Meningitis Screening: In order to screen that meningitic pain after aSAH was not due to from frank bacterial (septic) meningitis, CSF data will be reviewed from existing external ventricular drain (EVD) or CSF samples especially when there is fever and headaches documented in the electronic health record. The CSF culture result will also be analyzed to rule out any bacterial meningitis or ventriculitis. When CSF WBC is elevated and culture is negative for microorganisms, with persisting headache, these groups will be defined as 'aseptic' or inflammatory meningitis. Any patient who develops bacterial meningitis will be excluded from final headache analysis since the pathology will be different. The incidence of bacterial meningitis in SAH patients with EVD is < 1.0% and unlikely given the small sample size of this study. Also GBP medication is not expected to in any way increase the risk of bacterial meningitis based on our retrospective study and existing FDA safety data on GBP.

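### The fentanyl comparison for primary aim 1 makes no use of each patient's pre-dose fentanyl use; prespecifying that adjustment is a cheap gain in precision with 10 per arm

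*Combined protocol and SAP*

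**What the plan says.** Section 2 (Specific Aims) lists as its first primary aim "To compare the narcotic requirements among SAH patients experiencing headache treated with gabapentin or placebo for 7 days".

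The analysis of that aim is in C.6: "We will compare the NPS, patient satisfaction score and the fentanyl requirement among the GBP and placebo group", followed by "We will use 2 sample t test or Wilcoxon rank sum test". No baseline value, change score or covariate is named. C.6 mentions regression once: "If there is difference more than 5 %, we will use regression modeling to analyze the data". That sentence follows the one on aseptic meningitis, vasospasm and DIND, depends on an observed difference, and names no covariate. Read naturally, it does not cover fentanyl.

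On the time before treatment, C.2 allows randomisation up to 72 hours after admission and starts study medication at about 9:00 AM "on the morning following randomization into the trial to allow for documentation of the baseline average NPS". That baseline serves the rule on a 50% fall in pain score. Section 2 describes the background treatment as an existing standard of care with narcotics and NSAIDs, and C.2 puts as-needed intravenous fentanyl first in it.

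On recording, C.2 says that after consent and enrolment "a data collection sheet will be recorded by nursing to summate the NPS scores every 24 hours along with the SOC pain management plan". C.4 (Narcotic Requirement) adds "Total daily requirement of fentanyl for head and neck pain will be calculated every day". No section defines or uses a pre-dose fentanyl amount.

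**The concern.** As-needed opioid use can vary widely between patients for reasons unrelated to the study drug, and C.3 does not exclude prior opioid use. A patient's own use before the first dose is a natural predictor of use afterwards. The plan waits overnight to obtain such a baseline for pain but not for its other primary outcome.

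With 10 patients per arm, two things are at stake. Between-patient variation that a baseline could explain stays in the error term. A chance difference between arms in pre-dose use also passes, in part, into the estimated treatment difference. If a covariate is wanted, it has to be fixed in advance; one added after unblinding would carry little weight.

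**Working it through.** **Inputs from the documents.** 10 per arm and 80% power (C.7); two-sided alpha 0.05 (C.6); SD 5.84, for the pain score only (C.7). No SD for fentanyl and no pre/on-treatment correlation is given. Effects are therefore in SD units, and rho is an assumption shown over a range.

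**The plan's own figure.** C.7 states that fewer than 10 are needed for a 25% difference. This concerns pain score and satisfaction, not fentanyl, and gives no reference mean. With n per arm = 2(1.960 + 0.842)² × 5.84²/Δ² ≈ 535/Δ², n of 9 or fewer needs Δ ≥ 7.7 points, that is a mean daily total of about 7.7/0.25 ≈ 31 or more. On a 0–10 daily average, 25% of 10 is 2.5 points and n = 86 per arm. The stated figure can be neither confirmed nor refuted, and it does not bear on the fentanyl comparison.

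**Step 1: planned test.** For a true 1-SD difference, the noncentrality is 1/√(2/10) = 2.24 on 18 df. Power is 56%. The difference detectable at 80% power is 1.32 SD.

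**Step 2: adjusted test.** ANCOVA leaves a fraction 1 − rho² of the variance, uses 17 df, and pays for chance baseline imbalance by a factor 1 + 1/(2n − 4) = 1 + 1/16 = 1.0625. The noncentrality is 1/√[(1 − rho²) × 0.2 × 1.0625]. The last column is 10/(1 − rho²), which ignores the lost degree of freedom and the imbalance factor.

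| rho (assumed) | 1 − rho² | Noncentrality | Power, formula | Power, simulated | Equivalent n per arm |
|---|---|---|---|---|---|
| 0 | 1.00 | 2.17 | 53% | 53% | 10 |
| 0.3 | 0.91 | 2.27 | 57% | 58% | 11.0 |
| 0.5 | 0.75 | 2.51 | 66% | 66% | 13.3 |
| 0.6 | 0.64 | 2.71 | 72% | 73% | 15.6 |
| 0.7 | 0.51 | 3.04 | 82% | 82% | 19.6 |

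Formula and simulation agree to about one point. In simulation at rho 0.3, 0.5 and 0.7, type I error was about 5% for the unadjusted and the adjusted test alike.

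**Step 3: chance imbalance.** The standard error of the between-arm difference in pre-dose use is √(2/10) = 0.447 SD. P(|difference| > 0.5 SD) = P(|Z| > 0.5/0.447 = 1.12) = 26%. An imbalance of 0.5 SD shifts the unadjusted estimate by rho × 0.5 SD: 0.25 SD at rho 0.5 and 0.35 SD at rho 0.7.

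**Step 4: why not a change score.** Its variance factor is 2(1 − rho), which exceeds 1 when rho is below 0.5. At rho 0.3 simulated power was 44%, against 56% for the unadjusted test. ANCOVA does not carry that risk.

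**The case against.** The strongest reply is that nothing is wrong with the planned test, and that a small study meant to inform a larger one need not optimise precision. The first half stands. A reader might infer that the unadjusted comparison is biased or has an inflated error rate; randomisation rules that out, and the simulations show no inflation.

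A reader might also infer that every patient has a full 24-hour opioid record on the standard regimen before the first dose. The documents do not say so. The 72 hours in C.2 is an upper limit, so a patient randomised on the evening of admission has less than a day of record. C.1.a describes the site as a referral center, so some earlier opioid may have been given elsewhere. C.4 counts fentanyl for head and neck pain only, and records from before enrolment may not separate it by indication. That patients can be on the regimen before dosing, and that an amount is recoverable, is a well-supported inference only. Incomplete or less specific pre-dose data would lower rho and so the gain. They would not bias the comparison, because the value precedes study drug in both arms.

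The gain is not assured. C.1.b reports that pain rose slowly to a maximum around day 5, so early use may predict a 7-day average only modestly. At rho 0.3 there is almost no benefit, and near zero there is a small loss, so the adjustment is not free.

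Finally, a reader might argue that one or two heavy users would decide the result. That applies to a comparison of means. C.6 also offers the Wilcoxon test, in which an extreme value counts only through its rank.

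**Conclusion.** The point holds as a low-cost improvement in efficiency, not as a flaw in validity. The only planned fentanyl comparison is unadjusted, and no use is made of pre-dose fentanyl.

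If rho lies between 0.5 and 0.7, adjustment raises power for a 1-SD effect from 56% to between 66% and 82%, a gain of 10 to 26 points. This is roughly what 3 to 10 more patients per arm would bring. The downside at rho near zero is about 3 points.

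These figures rest on an assumed rho, on effects in SD units, and on linear ANCOVA with normally distributed outcomes. A rank-based version would give somewhat different values, so they show the order of the gain rather than the exact power of the proposed analysis. The 26% chance of an imbalance above 0.5 SD does not depend on rho; the effect of that imbalance on the estimate does.

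**What to change.** Prespecify in C.6, before any unblinding:

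- **Outcome:** mean daily fentanyl for head and neck pain over the 7 days.
- **Covariate:** pre-dose fentanyl as an hourly rate over the available in-house window, up to 24 hours before the first study dose. A rate handles patients with shorter records.
- **Analysis:** rank-based ANCOVA of the outcome on arm and covariate. Ranks avoid a log(1 + x) transformation, whose result would depend on the unit of dose.
- **Sensitivity analysis:** the planned unadjusted t or Wilcoxon test.

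Use fentanyl alone, as C.6 does, so that no opioid conversion rule is needed.

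The cost is one figure per patient from the medical record, one degree of freedom, a short addition to C.6, and about 3 power points if the correlation proves to be near zero. A rank-based analysis also gives a test rather than a difference in micrograms, so the unadjusted difference and its 95% confidence interval should be reported beside it.
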